5 INTRODUCTION

Treatment of active (symptomatic) multiple myeloma (MM) generally consists of anti-myeloma therapy with supportive care to alleviate symptoms of the disease and side effects of treatment ([About Multiple Myeloma 2016](#)). In addition to autologous stem cell transplant (ASCT), six drug classes are used in treatment: immunomodulatory drugs (IMiDs), proteasome inhibitors (PIs), chemotherapy, histone deacetylase inhibitors, steroids, and most recently, monoclonal antibodies. Recent treatment advances for the treatment of patients with relapsed or refractory MM have demonstrated significant improvements in response rates, duration of response, and long-term survival compared to traditional chemotherapy or other standards of care.

Despite these advances, MM remains incurable; more than 90% of patients relapse after treatment and succumb to the disease ([Hoyos and Borrello 2016](#)). This highlights the need for new, additional therapies or combinations with novel mechanisms to fill these treatment gaps.

BION-1301 is a first-in-class humanized monoclonal antibody directed against a proliferation-inducing ligand (APRIL) currently in development for the treatment of relapsed or refractory MM. This clinical study is a first-in-human dose-finding study to evaluate the safety, tolerability, and initial clinical activity of BION-1301 administered as a single agent or with low-dose dexamethasone. The incidence of dose-limiting toxicities (DLTs), pharmacokinetic/pharmacodynamic (PK-PD) profile, and observed clinical activity will guide dose selection and further elucidate the mechanism of action of BION-1301.

5.1 Rationale for Targeting APRIL in Multiple Myeloma

The rationale to target APRIL in the treatment of advanced MM is supported by the following:

- APRIL is produced by cells in the bone marrow niche and triggers BCMA to drive proliferation and survival of human MM cells ([Tai et al. 2016](#)).
- APRIL has been shown to drive expression of the immune checkpoint inhibitor programmed cell death ligand-1 (PD-L1), interleukin-10 (IL-10), vascular endothelial growth factor (VEGF) and transforming growth factor beta (TGF- β), forcing an immunosuppressive phenotype on BCMA positive cells ([Tai et al. 2016](#)).
- APRIL induces resistance to lenalidomide, bortezomib, and other standard-of-care drugs ([Tai et al. 2016](#)).
- Patients with MM have elevated APRIL serum levels which have been correlated with poor prognosis ([Lascano et al. 2015](#)).
- BION-1301 has been shown to target MM cells in a tumor-protective bone marrow microenvironment providing preclinical proof of concept ([Tai et al. 2016](#)).

Therefore, the mechanism-of-action and evidence of *in vitro* and *in vivo* antitumor activity strongly support APRIL as a rational target for the treatment of relapsed or refractory MM.

5.2 BION-1301

BION-1301 is a humanized IgG4 monoclonal antibody directed against APRIL in development for the treatment of relapsed or refractory MM.

Proof-of-concept studies in murine models supported by *in vitro* and *ex vivo* data suggest BION-1301 initiates a productive antitumor response with no/ limited toxicity observed in non-human primate studies.

5.2.1 Summary of Nonclinical Studies

BION-1301 does not bind to mouse APRIL; as such the murine parental antibody, hAPRIL.01A, served as the surrogate for murine models. hAPRIL.01A was characterized *in vitro* and *in vivo* and shown to bind to APRIL, fully block APRIL binding to BCMA and TACI, and block tumor development in a multiple myeloma humanized severe combined immunodeficiency (SCID) mouse model.

BION-1301, derived from hAPRIL.01A by CDR-grafting, exhibited similar binding and blocking characteristics in biochemical assays and cellular assays. To further establish PD activity, BION-1301 was shown to suppress T cell-independent (TI) B cell responses in mice and cynomolgus monkeys.

A series of nonclinical studies in nonhuman primates evaluated the pharmacology, PK, and toxicology of BION-1301. The cynomolgus monkey was selected as the relevant toxicity species for the GLP safety evaluation of BION-1301 based on sequence homology between cynomolgus APRIL and human APRIL. No toxicity was observed in the toxicology studies. A drop in production of immunoglobulins (IgA, IgG and IgM) was observed following dosing with BION-1301 to cynomolgus monkeys; this was not considered an adverse effect and confirmed APRIL blockade is relevant for plasma cells.

Safety pharmacology studies indicated no effects on the cardiovascular or central nervous systems; there were no effects on vital organs noted with BION-1301. Human and cynomolgus monkey tissue cross-reactivity showed no staining with BION-1301 in any tissue panel examined.

The anticipated PK of BION-1301 in humans has been predicted by modeling of the available nonclinical data. The predicted human systemic plasma C_{max} and AUC_t for an intravenous (IV) dose of 50 mg are [REDACTED], respectively.

[REDACTED]

[REDACTED] Overall, nonclinical studies support use of BION-1301 in humans at the proposed dose levels. A complete summary of nonclinical information on BION-1301 is provided in the Investigator's Brochure (IB).

5.2.2 Summary of Clinical Studies

ADU-CL-16 is the first study to investigate the safety and tolerability of BION-1301 in humans. Preliminary safety data (as of 15AUG2018) are available for 11 subjects administered BION-1301 at dose levels between 50 and 450 mg. Treatment-related treatment-emergent adverse events (TEAEs) were reported for 3 of the 11 subjects, which included arthralgia (reported for 2 subjects) and wheezing. The treatment-related TEAE of wheezing was assessed as Grade 3 in severity and was considered the principal symptom of a possible infusion-related reaction; the subject was discontinued from study drug.

The most current information related to anticipated safety risks based on nonclinical information and/or predicted by mechanism of action is provided in the IB.

5.2.3 Risk-benefit Assessment

Since essentially all patients with MM eventually relapse, there is an unmet medical need to provide new therapies with novel mechanisms of action, such as BION-1301. Blocking APRIL provides a novel approach to inhibit MM cell proliferation and survival, overcome drug resistance, and prevent immune suppression. BION-1301 induces antitumor activity *in vitro* and *in vivo*, and may confer therapeutic benefit in the treatment of MM.

Nonclinical toxicology studies with BION-1301 showed no signs of toxicity after single or repeat dosing of BION-1301 in cynomolgus monkeys. Decreases in IgA, IgM and IgG were observed following BION-1301 administration; however no adverse effects were associated with the pharmacologic activity of BION-1301. However, as observed with other treatments for MM, it is not known whether BION-1301 could further compromise the immune system, thereby leading to an increased risk of infection. Based on evidence from nonclinical studies, the risk/benefit assessment of BION-1301 is expected to be favorable in adults with relapsed or refractory MM.

Since this is the first study to investigate administration of BION-1301, there may be unexpected toxicities. The risk to subjects in this trial may be mitigated by compliance with the eligibility criteria and study procedures, close clinical monitoring, and applying dose modification/dose delay criteria. To mitigate tolerability issues and the potential for infusion-related reactions, the use of supportive care by Investigators should be used as needed.

Available data indicate BION-1301 has the potential to exhibit clinical activity in the treatment of MM; nonclinical data identified no undue safety issues that would preclude use in adults with relapsed or refractory MM. To date, BION-1301 has generally been well-tolerated in the current clinical study. The hypothesized mechanism of action reinforced by nonclinical data therefore supports clinical investigation with BION-1301 in adults with relapsed or refractory MM.

5.2.4 Dose Selection Rationale

The recommended BION-1301 starting dose and dosing schedule for this first-in-human study are based on nonclinical safety, tolerability, and PK-PD data obtained from the non-GLP PK-PD

and GLP toxicology studies in cynomolgus monkeys. The dose was selected using a minimum anticipated biological effect level (MABEL) approach.

The maximum recommended starting dose takes into consideration the novel mechanism of action of BION-1301 and the study population of advanced cancer patients with relapsed/refractory MM. Since APRIL is a soluble ligand driving proliferation and survival of MM cells (Tai et al. 2016), the extent and duration of APRIL blockade by BION-1301 needed to impact MM cells in patients is not defined with the same approach utilized with therapeutic antibodies which function via direct cytotoxicity. The pharmacology of APRIL antagonism suggests that the vast majority of APRIL should be bound in order to achieve a clinical effect. The duration of Full Target Engagement (TE; reduction of free APRIL in blood, Section 7.1.1.1) at the initial dose should be long enough to provide a potential for clinical benefit but short enough to ensure subject safety. A Full TE duration of one day or less is unlikely to represent a potential clinical benefit, therefore the Full TE duration is conservatively set to be 2 days. This will allow for a potential clinical benefit without unnecessary risk. Using PK-PD modeling, a fixed dose of 50 mg is predicted to reach Full TE for approximately 48 hours. Serial serum measurements of free APRIL to determine TE are included in this study. These sampling occasions allow monitoring of maximum TE.

Nonclinical data indicate weekly IV administration of BION-1301 to cynomolgus monkeys was well tolerated at doses ≤ 100 mg/kg. The starting dose of 50 mg proposed for the Phase 1 clinical trial has at least [REDACTED]

[figure not shown]
[REDACTED] in cynomolgus monkeys. Thus, adequate safety factors exist to support the proposed human IV doses of BION-1301 to adults with relapsed or refractory MM. The maximum dose administered will not exceed 2700 mg. The maximum dose level was selected based on available tolerability and PK-PD data from the ongoing ADU-CL-16 clinical study. Predicted exposure (based on AUC and C_{max}) at the 2700 mg dose level is [REDACTED] to the AUC and C_{max} observed at the NOAEL in cynomolgus monkeys.

5.2.5 Dose Schedule Exploration

A preliminary PK-PD model has been built based on data available from subjects dosed at the 50 mg, 150 mg, and 450 mg dose levels. The current PK-PD model incorporates an APRIL sink, which could represent APRIL binding to targets such as TACI or BCMA. Extrapolating from this preliminary model, Full TE would be achieved after approximately 3 months at a BION-1301 dose of 1350 mg dosed once every two weeks (Q2W), or after approximately 2 months when dosed once per week (QW). Dose levels higher than 1350 mg are anticipated to achieve Full TE earlier. Since longer-term QW dosing may pose a burden on patients, an extrapolation of the initial regime was performed. Results suggest that 3 to 8 weeks of QW dosing at 2700 mg followed by Q2W dosing at 1350 mg might achieve Full TE more quickly and maintain it over prolonged periods of time.

While data are not mature and modeling is still at an early stage, the overall trend of increasing target engagement with increasing dose and over time is confirmed in individual data plots (Figure 5-1), and is consistent with the conclusions derived from model extrapolations. Additional data will be used to further inform the PK-PD models, and will be used to support further dose escalation and schedule decisions.

Figure 5-1. Serum Free APRIL Levels Relative to Baseline over Time after BION-1301 Dosing

Source: ADU-CL-16 data (August 2018)

5.2.6 Rationale for BION-1301 + Dexamethasone in Multiple Myeloma

Dexamethasone is a synthetic glucocorticoid with anti-inflammatory, immunosuppressive, and analgesic properties. Dexamethasone is used in treatment regimens for various hematologic malignancies and as an antiemetic in conjunction with chemotherapy. Glucocorticoids used as part of combination regimens are a backbone of MM treatment in the first-line and relapsed/refractory settings ([Burwick and Sharma 2018](#)).

Monoclonal antibodies approved for the treatment of MM are often administered with dexamethasone or with dexamethasone-containing regimens. Daratumumab is approved for use in various dexamethasone-containing regimens (e.g. dexamethasone with lenalidomide, bortezomib or pomalidomide) for patients with varying degrees of previously-treated MM

([DARZALEX 2018](#)). Elotuzumab is approved for use in combination with lenalidomide and dexamethasone for the treatment of patients with MM who have received one to three prior therapies ([EMPLICITI 2017](#)). *In vitro*, APRIL blockade sensitizes MM cell lines to dexamethasone-induced apoptosis ([Tai et al. 2016](#)). Dexamethasone is thereby hypothesized to potentially add clinical benefit to BION-1301 therapy.

The low-dose dexamethasone regimen (40 mg QW) employed in Phase 2 of this study follows current management practices in MM ([Rajkumar and Kumar 2016](#)). The regimen is recommended based on results of a randomized trial where low-dose dexamethasone was associated with superior overall survival (OS) and significantly lower toxicity than a high-dose regimen ([Rajkumar et al. 2010](#)).

6 STUDY OBJECTIVES AND ENDPOINTS

The objectives of the study are to:

- Evaluate safety and tolerability of BION-1301 when administered as a single-agent or with low-dose dexamethasone (BION-1301+DEX)
- Identify the recommended Phase 2 dose (RP2D) and schedule of BION-1301 when administered as a single-agent
- Characterize the PK and PD profile of BION-1301
- Evaluate clinical activity of BION-1301 and BION-1301+DEX

The study has been designed with an appropriate study population, sufficient size, and duration to enable a preliminary assessment of safety and efficacy as related to the following specific endpoints:

ENDPOINTS:

Phase 1

- Incidence of DLTs, TEAEs, and changes in safety parameters
- PK parameters based on BION-1301 serum levels following a single dose and after repeated dosing
- Changes from baseline in soluble APRIL
- Relative reduction in serum and urine M-protein levels defined as the maximum percent reduction from baseline

Phase 2

- Objective response rate (ORR) based on International Myeloma Working Group (IMWG) uniform response criteria of stringent complete response (sCR), complete response (CR), very good partial response (VGPR), or partial response (PR)
- Relative reduction in serum and urine M-protein levels defined as the maximum percent reduction from baseline
- PFS defined as time from first dose of study drug to date of first tumor progression or death due to any cause
- OS defined as the time from first dose of study drug to date of death due to any cause
- Incidence of TEAEs, changes in safety parameters, and unacceptable toxicities
- PK parameters based on BION-1301 serum levels following a single dose and after repeated dosing

Exploratory Endpoints evaluated throughout the study as appropriate include:

- Duration of response (DOR) defined as the time from the first tumor assessment that supports the subject's ORR to the time of disease progression or death due to any cause
- Disease control rate (DCR) defined as the percentage of subjects with sCR, CR, VGPR, PR, or stable disease (SD) per IMWG criteria; or minimal response (MR) per European Group for Blood and Marrow Transplantation (EBMT) criteria.
- Change from baseline in soluble B cell maturation antigen (sBCMA; TNFRSF17) levels
- Changes in additional biomarkers and immune monitoring

7 INVESTIGATIONAL PLAN

7.1 Study Design

ADU-CL-16 is an open-label, multicenter, first in human, dose escalation study to evaluate the safety, tolerability, and PK-PD of BION-1301, a first-in-class monoclonal antibody targeting APRIL. The population for this study will consist of adults with relapsed or refractory MM whose disease has progressed after at least 3 prior systemic therapies. BION-1301 will be administered in 28-day cycles.

The study will be conducted in 2 parts as depicted in [Figure 7-1](#). Phase 1 will be conducted using a 3+3 dose escalation design and seeks to determine the RP2D by evaluating safety and tolerability and characterizing the PK-PD of BION-1301. Dose escalation decisions will be based on available safety, PK-PD, and efficacy data from all evaluable subjects in each cohort.

The dosing interval will be Q2W during initial dose escalation. Additional cohorts will be enrolled to evaluate QW dosing for up to 8 weeks, followed by Q2W dosing with the same or a lower dose. PK-PD data will be evaluated for each cohort to inform the dosing schedule to be evaluated in subsequent cohorts.

[figure not shown]
Once an RP2D and dosing schedule are identified, Phase 2 of the study will open and continue to evaluate the safety and preliminary efficacy of BION-1301 administered as a single agent or with low-dose dexamethasone.

Additional guidelines specific to Phases 1 and 2 of the study are provided in [Sections 7.1.1](#) and [7.1.2](#), respectively. A schedule of visits and procedures is provided in [Table 2-1](#).

Figure 7-1. ADU-CL-16 Study Schema

Screening Period Confirm eligibility Up to 28 days	Treatment Period (28-day Dosing Cycles) Until disease progression or unacceptable toxicity BION-1301 (IV infusion) +/- Dexamethasone (40 mg QW PO; Phase 2 only)	Follow-Up Period (Q12W) Safety reporting Subsequent cancer treatment Survival
--	---	---

Study Population & Enrollment Plan:

7.1.1 Phase 1: Dose Escalation

Phase 1 of the study seeks to evaluate the safety and tolerability of BION-1301 when administered as a single agent. Initially, BION-1301 will be administered at the 50 mg dose level; subsequent dose escalations will follow both safety and pre-specified dose escalation rules (Section 7.1.1.1).

Subjects within a dose cohort will be evaluated through Cycle 1 for DLTs (28-day evaluation period) and PK-PD parameters (14-day evaluation period). Dose escalation decisions will be based on available safety, PK-PD, and efficacy data from all evaluable subjects in each cohort.

The Safety Review Team (SRT) convened for the study, will consist of the Investigators who enrolled subjects in the study, Medical Monitor, and Sponsor representatives. Dose escalation and reduction decisions, additional enrollment specifications, and recommendation of the RP2D(s) and dosing schedule for expansion will be made by the SRT. TEAEs, DLTs and safety data will continue to be reviewed by the SRT throughout the study.

7.1.1.1 Enrollment Plan and Dose Escalation Rules

During the dose escalation part of the study, cohorts will be enrolled and treated with BION-1301 following a 3+3 dose escalation plan (Table 7-1) until the RP2D (or MTD) is achieved. The Cycle 1 Day 1 dose must be staggered by at least 24 hours for the first 2 subjects dosed in each cohort.

Subjects will be considered evaluable for dose-escalation assessment if all scheduled doses were administered during Cycle 1, adequate PK-PD samples were collected at Cycle 1 Day 1 through Cycle 1 Day 15, and the DLT evaluation period (Cycle 1 Days 1-28) was completed; or the subject experienced a DLT-defining event. Evaluation of a cohort of at least 3 evaluable subjects is required prior to determining the dose for the next cohort. To proactively ensure at least 3 subjects are considered evaluable, a 4th subject may be enrolled and treated. No dose escalation decisions will be made until all subjects enrolled at a given dose level have completed the DLT evaluation period. If one subject experiences a DLT, the cohort will expand to 6 evaluable subjects.

Table 7-1. Phase 1: BION-1301 Enrollment and Dose Escalation Plan

BION-1301 Dose Cohort (proposed dose ¹)	0/3 subjects have DLT^{2,3}	1/3 subjects have DLT^{2,3}	≤1/6 subjects have DLT²	≥2 in a cohort have DLT²
1 (50 mg)	Escalate to Dose Cohort 2 per Dose Escalation rules	Expand to 6 evaluable subjects	Escalate to Dose Cohort 2 per Dose Escalation rules	MTD exceeded; de-escalate to Dose Cohort -1 ⁴
2 (150 mg)	Escalate to Dose Cohort 3 per Dose Escalation rules	Expand to 6 evaluable subjects	Escalate to Dose Cohort 3 per Dose Escalation rules	MTD exceeded; no further enrollment at dose level
3 (450 mg)	Escalate to Dose Cohort 4 per Dose Escalation rules	Expand to 6 evaluable subjects	Escalate to Dose Cohort 4 per Dose Escalation rules	MTD exceeded; no further enrollment at dose level
4 (1350 mg)	Escalate to Dose Cohort 5 per Dose Escalation rules	Expand to 6 evaluable subjects	Escalate to Dose Cohort 5 per Dose Escalation rules	MTD exceeded; no further enrollment at dose level
5 (2700 mg)⁵	Expand to 6 evaluable subjects	Expand to 6 evaluable subjects	Maximum dose reached	MTD exceeded; no further enrollment at dose level

1. Dose levels may be escalated up to maximum 3-fold increases; actual dose determined empirically by SRT based on available safety, PK-PD, and efficacy data. Additional incremental dose levels (either increased or decreased) may be investigated.
 
2. DLT evaluation period is 28 days after first dose of BION-1301 (Cycle 1).
 
3. If a 4th subject is enrolled, all 4 subjects must complete DLT evaluation period. If 1/4 subjects has DLT, expand to 6 evaluable subjects.
 
4. SRT will evaluate all available data and decide whether to initiate Dose Cohort -1 at a dose of 5 mg.
 
5. Evaluation of additional intermediate dose cohorts will follow the same 3+3 rules for dose cohort expansion. Dose level will not exceed 2700 mg.
 
DLT = dose-limiting toxicity; MTD = maximum tolerated dose; SRT = safety review team
				

To better understand the safety, tolerability, PK, and PD of BION-1301 administered as a single agent, additional subjects may be enrolled in previously cleared cohorts (for up to a total of 6 subjects per cohort), or additional cohorts of up to 6 subjects may be enrolled at intermediate dose levels before or while proceeding with further dose escalation, or to confirm the RP2D before proceeding to Phase 2.

7.1.1.1.1 Dose-limiting Toxicity Criteria

During Phase 1, the DLT evaluation period is defined as the first 28 days of treatment (Cycle 1). The occurrence of any of the toxicities presented in Table 7-2 will be considered a DLT unless clearly and incontrovertibly due to disease progression or extraneous causes. DLTs should be assessed and reported as directed in [Section 8](#).

Table 7-2. Criteria for Defining Dose-limiting Toxicities

Grade 5 event not clearly due to disease progression or extraneous causes
Hematologic toxicity defined as: 
 • Febrile neutropenia of any duration • Grade 4 neutropenia or thrombocytopenia that persists for >7 days, or Grade 3 thrombocytopenia associated with bleeding
Serum chemistry values consistent with Hy's Law criteria (all 3 of the following must co-exist): 
 • Alanine aminotransferase or aspartate aminotransferase $\geq 3\times$ institutional upper limit of normal (ULN) • Total bilirubin $\geq 2\times$ ULN • Alkaline phosphatase $< 2\times$ ULN
Grade 3 or higher infusion-related reaction per NCI CTCAE v 4.03
Any other Grade 3 or higher non-hematologic toxicity except: 
 • Grade 3 nausea, vomiting, or diarrhea that persists <72 hours with adequate antiemetic and other supportive care • Grade 3 fatigue <7 days

Emergent safety data will continue to be evaluated on an ongoing basis by the SRT.

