7.1.1.1.2 Definitions for Dose Escalation and Identification of Recommended Phase 2 Dose

Target Engagement (TE) is defined as the reduction of free APRIL in blood relative to baseline. In this study, TE will be measured by the levels of free APRIL in the serum at trough, relative to study baseline. TE will be typically quantified on the basis of PK-PD modeling and simulation.

Full TE is defined as complete APRIL antagonism (i.e. >95%) in the blood at trough, as measured by the level of remaining free APRIL in serum. Full TE corresponds to levels of free APRIL of $\leq 5\%$ relative to baseline for the duration of the dosing cycle at steady state.

Mark TE is defined as complete APRIL antagonism (i.e. >95%) in bone marrow, as measured by the level of remaining free APRIL in bone marrow. Mark TE corresponds to levels of free APRIL of $\leq 5\%$. TE in bone marrow will be calculated using PK-PD modeling of available clinical data.

Maximum-tolerated Dose (MTD) is defined as the maximum dose at which an acceptable level of toxicity is observed, as evidenced by a DLT rate of < 33% (i.e. 0 DLT in 3 evaluable subjects or ≤ 1 DLT in 6 evaluable subjects). The MTD is one dose level lower than a dose level where a DLT rate $\geq 33\%$ was observed.

Recommended Phase 2 Dose is defined as the dose level at or below the MTD (or up to the highest dose tested if MTD is not reached) selected on the basis of a cumulative review of safety, tolerability, and clinical activity; may include PK, PD, and other available efficacy data.

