7.1.1.1.3 Dose Escalation Rules

Dose escalation decisions will be based on the totality of available safety, efficacy, PK and PD data, complemented with PK-PD modeling if data allow. Dose escalation decisions and identification of the MTD will be made by the SRT. The following dose escalation rules will be followed:

- If DLTs are observed a traditional step-up step-down ruleset (3+3) will be triggered; escalation will be stopped if the MTD has been reached. Subjects who were enrolled into the MTD Dose Cohort and are tolerating treatment may continue with dosing at that dose level.
- If two or more subjects in Dose Cohort 1 have a DLT, new subjects will be enrolled into Dose Cohort -1, at a dose of 5 mg. Subjects who were enrolled into Dose Cohort 1 and are tolerating treatment may continue with dosing at the Dose Cohort 1 dose. Following completion of Dose Cohort -1, additional cohorts may be evaluated using the 3+3 dose escalation plan as outlined above, at dose levels not to exceed 3-fold increases and below 50 mg.
- Dose escalations will be selected such that the next dose level will target an increase of full TE duration by a maximum 3-fold, which is expected to generally translate to a 3-fold increase in dose (no higher increases in dose will be used). Dose escalations will account for observed safety in the preceding cohort and will not exceed safety factors based on the NOAEL established in non-human primates, but would allow for appropriate dose escalation to potentially therapeutically effective dose levels.
- Escalation may be stopped if BION-1301 exposure or the level of TE has not increased and/or is not expected to increase to a clinically relevant extent.

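### The bleeding clause in Table 7-2 names only Grade 3 thrombocytopenia, so a short Grade 4 event with Grade 1-2 bleeding can escape the DLT count, and expansion to 6 then becomes discretionary

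*Protocol*

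**What the plan says.** Protocol Section 7.1.1.1.1 makes an event a DLT only if it appears in Table 7-2 and is not clearly due to progression or extraneous causes. The thrombocytopenia criteria are "Grade 4 neutropenia or thrombocytopenia that persists for >7 days, or Grade 3 thrombocytopenia associated with bleeding". Two other rows of the table are open-ended upwards: "Grade 3 or higher infusion-related reaction per NCI CTCAE v 4.03" and "Any other Grade 3 or higher non-hematologic toxicity except" (followed by short exceptions for gastrointestinal events and fatigue). The SAP reports DLTs but gives no definition of its own.

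The DLT count drives binding rules:

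- Section 7.1.1.1: "If one subject experiences a DLT, the cohort will expand to 6 evaluable subjects". At 0/3, Table 7-1 sends Cohorts 1-4 on to the next dose under the escalation rules. Cohort 5, and Cohort 6 in SAP Table 1, expand to 6 at both 0/3 and 1/3.
- Section 7.1.1.1, evaluability: "Subjects will be considered evaluable for dose-escalation assessment if all scheduled doses were administered during Cycle 1", with adequate PK-PD samples and a completed DLT period. Otherwise a subject is evaluable only through a DLT.
- Section 7.1.1.1.2 defines an acceptable dose by "0 DLT in 3 evaluable subjects or ≤ 1 DLT in 6 evaluable subjects".

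Discretion sits beside these rules. Section 7.1.1.1 says that "additional subjects may be enrolled in previously cleared cohorts (for up to a total of 6 subjects per cohort", and Section 7.1.1.1.3 says "Dose escalations will account for observed safety in the preceding cohort".

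**The concern.** A DLT definition should not rank severity backwards. Here Grade 3 thrombocytopenia with minor bleeding scores one DLT, while Grade 4 thrombocytopenia with the same bleeding can score none if it resolves within a week. The protocol gives no reason for the reversal. Since neighbouring rows write *or higher* where it is meant, this looks like a drafting omission.

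What is at stake is an obligation. In a first-in-human study without a data monitoring committee (Section 7.6.10), the pre-specified count is the main safeguard that does not depend on judgement. A subject with this event who received all Cycle 1 doses and meets the other evaluability conditions enters the tally as a non-DLT. A subject who missed a Cycle 1 dose because of it becomes non-evaluable and leaves the tally. Neither outcome forces expansion. The hold that Section 7.4.5.1 attaches to a DLT is also not triggered. Section 7.1.1.2 requires a dose to be cleared at Q2W before it is given weekly, so a miscounted 0/3 can carry over to the QW schedule.

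**Working it through.** **1. Row check.** Take Grade 4 thrombocytopenia lasting 7 days or less with Grade 1-2 bleeding, scored at peak grade.

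- Grade 5 row: not met.
- Febrile neutropenia: not met.
- Grade 4 beyond 7 days: not met.
- Grade 3 with bleeding: not met at peak grade.
- Hy's Law and infusion reaction: not met.
- Other non-hematologic toxicity: requires Grade 3 or higher, so neither the platelet event nor the bleeding qualifies.

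The gap stops there. Fatal bleeding meets the Grade 5 row. Grade 3 or higher bleeding meets the non-hematologic row, if bleeding is classed there. Grade 4 beyond 7 days meets the hematologic row.

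**2. The plan's own rule.** The acceptable DLT rate is below 33%: 1/6 = 16.7% passes and 2/6 = 33.3% fails, as Section 7.1.1.1.2 states. An uncounted event can turn 2/6 into 1/6, or 1/3 into 0/3.

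**3. Average effect on clearing a dose, Cohorts 1-4.** Let p be the true DLT rate including the gap event and q the gap-event rate. The documents give neither, so both are assumed. For a counted rate r,

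P(clear) = (1 − r)³ + 3r(1 − r)⁵.

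With the corrected row, r = p. With the current row, r = p − q if the subject counts as a non-DLT, or r = (p − q)/(1 − q) if the subject is non-evaluable and another must be enrolled. For p = 0.33, the corrected row gives 0.67³ + 3(0.33)(0.67⁵) = 0.301 + 0.134 = 0.434.

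| p | q | Corrected row | Current row, replaced | Current row, non-DLT |
|---|---|---|---|---|
| 0.33 | 0.005 | 0.434 | 0.441 | 0.444 |
| 0.33 | 0.01 | 0.434 | 0.448 | 0.454 |
| 0.33 | 0.02 | 0.434 | 0.461 | 0.474 |
| 0.20 | 0.005 | 0.709 | 0.717 | 0.719 |
| 0.20 | 0.01 | 0.709 | 0.726 | 0.730 |
| 0.20 | 0.02 | 0.709 | 0.744 | 0.752 |

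**4. Cohort 5 and SAP Cohort 6.** These expand at 0/3 anyway, so P(clear) = (1 − r)⁶ + 6r(1 − r)⁵. At p = 0.33 the corrected row gives 0.358. The current row gives 0.365, 0.371 and 0.386 (replaced) or 0.368, 0.378 and 0.399 (non-DLT) for the same q. The effect arises only through the six-subject count.

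**5. Effect when the event occurs.** Suppose one of the first three subjects has the gap event and the other two have no DLT. Now let p be the DLT rate in further subjects.

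- Corrected row: 1/3, expand, and clear only if the next three have no DLT: (1 − p)³ = 0.729, 0.512, 0.301 at p = 0.10, 0.20, 0.33.
- Current row, replaced: (1 − p) + p(1 − p)³ = 0.973, 0.902, 0.769.
- Current row, non-DLT: the dose clears with no further subject required.

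Under the model in step 3 this scenario has probability of about 3q(1 − p)². At p = 0.20 that is 1.0%, 1.9% and 3.8% of cohorts for q = 0.005, 0.01 and 0.02. None of these figures models SRT discretion.

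**The case against.** Several points on the other side stand.

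- **Platelets pass through Grade 3.** A count falling to Grade 4 and recovering from it is at Grade 3 on the way. Bleeding at either point literally meets the row, and Table 7-2 does not say that only the peak grade counts. This is why the point is limited to peak-grade scoring or bleeding confined to the Grade 4 interval. It does not remove the point, because sites could then score the same event differently.
- **The SRT can act without a DLT.** It reviews all safety data, may expand a cleared cohort to 6 and must weigh observed safety before escalating. None of these provisions obliges it to expand.
- **Medical Monitor controls remain.** A reader might infer that Section 7.4.5.1 no longer protects such a subject. It does in part: after any AE hold, dosing generally waits for Grade 1 or baseline, earlier resumption needs Medical Monitor consultation, and dose reductions need approval. Only the DLT-triggered hold, with its consultation before resuming, is lost.
- **The event is probably rare.** The monkey studies showed no toxicity (Section 5.2.1). The related events in the first 11 subjects were arthralgia and wheezing (Section 5.2.2). Entry requires platelets of at least 75,000/µL (Section 7.3.1).
- **Little was left to affect.** Subjects had been dosed at 50 to 450 mg by 15 August 2018, before Amendment 2 of 13 November 2018, on which the SAP is based. The main three-subject decision still open was the 2-fold step from 1350 to 2700 mg, plus any intermediate cohorts.

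**Conclusion.** The point holds in its limited form. On a peak-grade reading, or where the bleeding falls only within the Grade 4 interval, the table leaves out a more severe event than one it includes, and nothing else in the protocol or SAP repairs this. The consequence is that a mandatory expansion becomes discretionary in Cohorts 1-4 and intermediate cohorts, and that 2/6 can read as 1/6.

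The average effect is small: about 0.7 to 4 percentage points on the chance of clearing a dose at an assumed 33% DLT rate, and about 0.9 to 4.3 points at 20%, for assumed event rates of 0.5% to 2%. The effect is large only in the uncommon cohort where the event actually occurs.

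A reader might infer that every Grade 4 thrombocytopenia with bleeding goes uncounted, or that a dose in this study was cleared wrongly. The documents support neither. Other rows catch longer, Grade 3 or higher, or fatal cases, and neither document reports an event of this kind.

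**What to change.** In Table 7-2, insert *or higher* after Grade 3 in the bleeding clause, so that it reads *Grade 3 or higher thrombocytopenia associated with bleeding*. The sponsor's medical lead should confirm that this is the intent. The change then carries through to the DLT hold in Section 7.4.5.1. It costs two words. The downside is an occasional extra DLT, so that a cohort could expand or stop on an event the current row leaves out.

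The study was terminated on 07 May 2019 and the SAP is dated 18 July 2019, so the wording change matters mainly for reuse of the table. For the completed Phase 1, report DLTs under the definition in force when subjects were treated. A supplementary flag for events meeting the corrected clause is optional. SAP Sections 9.1 and 9.2 already plan Grade 3 or higher TEAE summaries, full AE listings, platelet grade shift tables and laboratory listings, and these should show such an event among 21 subjects.
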